10.4.4 Handling of missing values/censoring/discontinuations

A patient who has not progressed or died at the date of the analysis cut-off would have his/her PFS and OS censored at the time of the last adequate assessment before the cut-off date. Any disease assessment indicating response status other than “unknown” or “not done” is considered an adequate response assessment.

No imputation of missing values will be performed on any of the efficacy endpoints.

10.4.5 Supportive analyses

Not applicable.

10.5 Secondary objectives

10.5.1 Key secondary objective(s)

The key secondary objective of this study is to assess Overall Response (OR) of Partial Response (PR) or greater based on local investigator assessment.

For patients with solid tumors the assessment criteria will be RECIST 1.1 and will include responses of CR and/or PR. For hematologic tumors other appropriate hematological response criteria will apply and are included in the appendices.

The overall response rate (PR or greater) and its 95% exact confidence interval will be provided for each patient group.

10.5.2 Other secondary efficacy objectives

The secondary efficacy objectives of the study:

- To assess progression free survival (PFS) based on local investigator assessment per RECIST 1.1 or other appropriate hematological response criteria
- To assess overall survival
- To assess duration of response (DOR) based on local investigator assessment per RECIST 1.1 or other appropriate hematological response criteria

The secondary efficacy variable progression free survival (PFS) is defined as the time from the date of first dose to the date of first documented disease progression or relapse or death due to any cause.

PFS will be summarized and graphed using the Kaplan-Meier product-limit method for each patient group. Patients who drop-out without progression will be censored at the time of last adequate assessment. The estimates of the 25th, median, 75th percentiles of the PFS and their 95% confidence intervals will be provided, if applicable.

Overall survival (OS) is defined as the time from the date of first dose to the date of death due to any cause. If a patient is not known to have died, survival time will be censored at the date of the last contact.

OS will be summarized and graphed using the product-limit method as above.

The duration of response (PR or greater) applies only to patients whose best response was PR or greater. For patients with solid tumors the assessment criteria will be RECIST 1.1 and will include responses of CR and/or PR. For hematologic tumors other appropriate hematological response criteria will apply and are included in the appendices. The duration of response is defined as the time from the first documented response to the date first documented disease progression or relapse or death due to any cause. The duration of response will be summarized descriptively for each patient group.

If the study primary efficacy endpoint is not met, Novartis may decide not to conduct some of the above secondary efficacy analyses but instead provide those endpoints in listings only.

10.5.3 Safety objectives

For all safety analyses, the Safety Set will be used. All listings and tables will be presented by patient groups.

The assessment of safety will be based mainly on the frequency of adverse events and on the number of laboratory values that fall outside of pre-determined ranges. Other safety data (e.g., electrocardiogram, vital signs) will be considered as appropriate. All safety data will be listed.

The safety summary tables will include only assessments collected no later than 30 days after study treatment discontinuation. Those collected later than 30 days after study treatment discontinuation will be flagged in listings.

10.5.3.1 Analysis set and grouping for the analyses

10.5.3.1.1 Adverse events (AEs)

All adverse events recorded during the study will be summarized. The incidence of treatment-emergent adverse events (new or worsening from baseline) will be summarized by presenting the number and percentage of patients by system organ class and/or preferred term, maximum severity (based on CTCAE v4.03), type of adverse event, and relationship to the study treatment. In addition, adverse events of related nature may be analyzed by categories regrouping the relevant preferred terms, as appropriate. Adverse events that occurred on the same subject in the same system organ class and/or preferred term will be counted only once for the one with the highest severity.

Deaths reportable as SAEs and non-fatal serious adverse events will be listed by patient and tabulated by type of adverse event and patient group.

10.5.3.12 Laboratory abnormalities

All laboratory values will be converted into SI units and the severity grade will be calculated using appropriate common terminology criteria (CTCAE v4.03).

A severity grade of 0 will be assigned when the value is within normal limits. For lab parameters for which severity grades are determined both through normal limits and absolute cut-offs, in the unlikely case when a local laboratory normal range overlaps into the higher (i.e. non-zero) CTCAE grade, the laboratory value will still be taken as within normal limits and assigned a CTCAE grade of zero.

A listing of laboratory values will be provided by laboratory parameter, patient, and visit. A separate listing will display notable laboratory abnormalities (i.e., newly occurring CTCAE grade 3 or 4 laboratory toxicities). Lab values collected later than 30 days after study treatment discontinuation will be flagged in the listings

The following by-group summaries will be generated separately for hematology, and biochemistry parameters:

[figure not shown]
- shift tables using CTCAE grades to compare baseline to the worst on-treatment value
- for laboratory tests where CTCAE grades are not defined, shift tables using the low/normal/high/(low and high) classification to compare baseline to the worst on-treatment value.
- listing of all laboratory data with values flagged to show the corresponding CTCAE grades and the classifications relative to the laboratory normal ranges.

10.5.3.13 Other safety data

Summary statistics for data from other tests will be provided, notable values will be flagged, and any other information collected will be listed as appropriate.

Descriptive summary statistics will be provided for :

- Electrocardiograms: changes from baseline to last available ECG results
- Cardiac imaging: number and percentage of patients with notable LVEF values
- Vital signs: number and percentage of patients with at least one post-baseline vital sign abnormality
- ECOG performance status: shift table comparing baseline to worst post baseline ECOG performance status.
- All other safety related procedures as required
- Listings with flagged notable values and any other information collected will be provided as appropriate.

[figure not shown]

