	Restart BGJ398 at the same dose level with maximal phosphate binder dosing if the patient did not receive maximal phosphate binder dosing for serum phosphorus > 7.0 mg/dL for > 7 days.
	Reduce one dose level of BGJ398 if the patient had received maximal phosphate lowering therapy for serum phosphorus > 7.0 mg/dL for > 7 days Or if patient had a one-time serum phosphorus of > 9.0 mg/dL. Restart BGJ398 with maximal phosphate binder dosing.
	It is recommended that phosphate binder dosing continues during BGJ398 dose interruptions for hyperphosphatemia and that serum phosphorus values be monitored frequently, e.g. every 2-3 days.
	Phosphate binder dosing should be held during the week off BGJ398 therapy each cycle (Days 22-28) for “3 weeks on / 1 week off” dosing regimen and during BGJ398 dose interruptions for non-hyperphosphatemia adverse events.

Worst Toxicity CTCAE v4.03 Grade (unless otherwise specified)	Recommended Dose Modifications any time during a cycle of therapy
Hypercalcemia Serum calcium grade 2	Hold BGJ398 dose until resolved to grade 1 or baseline: 
• if resolved within \leq 7 days after suspending BGJ398, maintain dose level• if resolved within $>$ 7 days after suspending BGJ398, \downarrow 1 dose level Discontinue patient from the study
Serum calcium \geq grade 3	
Nervous system disorders	
Neurotoxicity Grade 2	Omit dose of BGJ398 until resolved to CTCAE Grade \leq 1, then \downarrow 1 dose level of BGJ398
Grade \geq 3	Discontinue patient from study drug treatment
GI disorders	
Pancreatitis Grade \geq 2	Discontinue patient from study drug treatment
Diarrhea Grade 1	Maintain dose level of BGJ398, initiate anti-diarrheal treatment
Grade 2	
• Hold dose of BGJ398 until resolved to CTCAE Grade \leq 1• Optimize anti-diarrheal treatment, maintain dose level of BGJ398.• For reoccurrence of diarrhea CTCAE Grade 2, hold dose of BGJ398 until resolved to CTCAE Grade \leq 1, \downarrow BGJ398 by 1 dose level• Hold dose of BGJ398 until resolved to CTCAE Grade \leq 1• Optimize anti-diarrheal treatment• \downarrow BGJ398 by 1 dose level
Grade 3	
• For reoccurrence of diarrhea CTCAE Grade 3, despite optimal anti-diarrheal treatment, discontinue patient from study treatment.

Worst Toxicity CTCAE v4.03 Grade (unless otherwise specified)	Recommended Dose Modifications any time during a cycle of therapy

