7.1.3 End of treatment visit, including premature withdrawal and study discontinuation visit

7.1.3.1 End of treatment (EOT) visit

Patients who completely discontinue study treatment should be scheduled for an End of Treatment (EOT) visit within 14 days following the date study treatment is permanently discontinued, at which time all of the assessments listed for the EOT visit will be performed. For details of assessments, refer to [Table 7-1](#). If the decision to withdraw the patient occurs at a regularly scheduled visit, that visit may become the EOT visit rather than having the patient return for an additional visit.

[REDACTED]

An End of Treatment Phase Disposition eCRF page should be completed, giving the date and reason for stopping the study treatment. If a study withdrawal occurs, or if the patient fails to return for visits, the investigator must determine the primary reason for a patient's premature withdrawal from the study and record this information on the End of Treatment Phase Disposition eCRF page.

End of treatment/Premature withdrawal visit is not considered as the end of the study.

At a minimum, all patients who discontinue study treatment, including those who refuse to return for a final visit, will be contacted for safety evaluations during the 30 days following the last dose of study treatment.

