7.2.2.8 Cardiac assessments

7.2.2.8.1 Electrocardiogram (ECG)

A standard 12-lead ECG will be performed at screening, Day 1 and Day 15 of Cycles 1 and 2, at Day 1 of each subsequent cycle and at EOT according to the Visit Schedule outlined in [Table 7-1](#).

The interpretation of the tracing must be made by a qualified physician and documented in the ECG section of the eCRF. Each ECG tracing should be labeled with the study number, patient initials (if permitted by local regulations), Patient Number, date, and kept in the source documents at the study site. Only clinically significant abnormalities should be reported in the Adverse Events eCRF. Clinically significant abnormalities present when the patient signed informed consent should be reported on the Medical History eCRF page. Clinically significant findings must be discussed with the Novartis Medical Monitor prior to enrolling the patient in the study. New or worsened clinically significant findings occurring after informed consent must be recorded on the Adverse Events eCRF page.

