3.3 Study Treatment and other concomitant medications

Subjects receive BGJ398 at 125 mg once daily, 3 weeks on 1 week off. A complete treatment cycle is 28 days. There is no break between dosing cycles. For subjects who are unable to tolerate the protocol-specified dosing schedule, dose adjustments are permitted in order to allow these subjects to continue study treatment. Protocol section 6.3 provides the details.

In general, concomitant medications and therapies deemed necessary for the care of the subject are permitted (see Protocol Section 6.4.1 and 6.4.2), except as specifically prohibited (see Protocol Section 6.4.3). All medications, procedures and significant non-drug therapies (including physical therapy and blood transfusions) administered within 30 days prior to the administration of BGJ398 and through 30 days after the last dose of study treatment will be recorded in the corresponding CRF page.

Detailed summaries of study treatment and other concomitant medications are described in Section 5 below.

4 Patient demographics and other baseline characteristics

Demographic data, medical history, disease characteristics and other baseline characteristics are collected at the screening visit.

In general, the baseline value will be considered as the last measurement observed prior to the first dose of study treatment, and includes assessments taken on the date of the first dose of study treatment.

Unless specified otherwise, for continuous data, the mean, standard deviation, median, 25th and 75th percentiles, minimum, and maximum will be presented. For categorical data, frequencies and percentages will be presented.

Demographic characteristics

Demographic variables include:

- Age (years), age group (<65, ≥65-<75, ≥75 years)
- Sex (Male, Female – able to bear children, premenarche, post menopausal, sterile or child bearing age)
- Race (Caucasian, Black, Asian, Native American, Pacific Islander, Other)

Medical history

Number and percentage of subjects with relevant and/or current medical history/conditions will be summarized by categories of conditions. For ongoing conditions, grade of condition (i.e., 1-4) will also be summarized. Medical history/current medical conditions will be coded using Medical Dictionary for Regulatory Activities (MedDRA). The MedDRA version used for reporting the study will be specified as a footnote in the tables/listings.

Disease characteristics

Disease characteristics variables include:

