7.4 Laboratory evaluations

Laboratory assessment will be collected at screening and post baseline (at scheduled visits outlined in the protocol or as clinically indicated). The collected laboratory values will be converted into standard units and the severity grade will be calculated using CTCAE v4.03. A severity grade of 0 will be assigned when the value is within normal limits. For laboratory parameters where severity grades are determined both through normal limits and absolute cut-offs, in the unlikely case that a local laboratory normal range overlaps into the higher (i.e., non-zero) CTCAE grade, the laboratory value will still be taken as within normal limits and assigned a CTCAE grade of zero. Baseline is defined as the last non-missing measurement on or prior to the first BGJ398 treatment. On-treatment laboratory evaluations are defined as laboratory values collected post baseline and no later than 30 days after the last study treatment.

Abnormal on-treatment laboratory values will be summarized using shift tables (from baseline to any abnormal laboratory value post baseline) by each laboratory parameter at its worst severity grade. The number and percentage of subjects with abnormal laboratory values will be presented by CTCAE grade for each laboratory parameter that is CTCAE gradable. For laboratory parameters where CTCAE grades are not defined, shift tables using the low/normal/high/(low and high) classification to compare baseline to the worst on-treatment value will be provided. Listings of all laboratory values (Blood chemistry, Hematology/Coagulation parameters separately) in chronologic order will be provided for each laboratory parameter. Laboratory values collected more than 30 days after study treatment discontinuation will be flagged in the listing. A separate listing will also be provided for notable laboratory abnormalities (i.e., grade 3 or 4 laboratory toxicities post start of study treatment). In addition, other labs such as urinalysis and pregnancy tests will be listed separately. These presentations will be performed for the SS.

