7.5 Other safety evaluations

ECOG performance status will be summarized by visit for SS. The number and percentage of subjects in each score (0-5) will be displayed. In addition, the shift table of ECOG value from baseline to the worst score post baseline will be presented.

ECG values will be summarized descriptively by visit for the SS. Change from baseline for each collected parameter will also be summarized. The ECG parameters to be summarized include: QTcF, HR, PR, QT, and QRS.

Ophthalmic examinations will also be summarized for the SS. Abnormalities discovered via slit lamp, visual fields, fundoscopy examinations, optical coherence tomography, and fluorescein angiography will be summarized as a shift table for the worst cases and/or listed. In addition, visual acuity and intraocular pressure will be summarized descriptively by visit. Visual acuity will be presented using LogMAR (which is derived from Snellen equivalent using formula $\text{LogMAR} = [-\text{Log}_{10} \text{ (decimal acuity, i.e., Snellen equivalent)}]$). These summaries will be presented for right and left eyes separately.

Cardiac imaging evaluations will be summarized by visit for the SS. Change from baseline for LVEF will also be summarized. In addition, the incidence of cardiac abnormality will be provided.

Baseline for the safety evaluation is defined as the last non-missing measurement on or prior to the first BGJ398 dose.

8 Interim analyses

Scheduled interim analysis is planned for the primary endpoint of clinical benefit rate only as required by the Bayesian Hierarchical design. The first interim analysis performs after the first 30 patients have been dosed for at least 16 weeks or discontinued then every 13 weeks thereafter until study enrollment closure. After that, one CBR analysis will be done after database lock. Interim analyses may be performed more frequently dependent on enrollment rate to avoid over-enrollment in any of the disease groups. At each interim analysis, the groups will be evaluated for early futility and early success by comparing posterior quantities for the response rate to pre-specified early stopping criteria.

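### No planned table counts patients by worst post-baseline QTcF against the values the protocol itself uses, and no phosphorus table is tied to the mg/dL values in Table 6-3

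*Protocol*

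**What the plan says.** **ECG summaries.** Protocol 10.5.3.13 plans "Electrocardiograms: changes from baseline to last available ECG results". In the same list, LVEF and vital signs get a number and percentage of patients, and ECOG status gets a shift to the worst post-baseline score. SAP 7.5 plans a different ECG summary: "ECG values will be summarized descriptively by visit for the SS. Change from baseline for each collected parameter will also be summarized". SAP section 4 sets the default statistics for continuous data, which go beyond the mean: "median, 25th and 75th percentiles, minimum, and maximum will be presented". SAP 2.1, which lists departures from the protocol, records the change for vital signs but not the one for ECGs.

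**ECG timing.** ECGs are taken at screening and then on "Day 1 and Day 15 of Cycles 1 and 2, at Day 1 of each subsequent cycle and at EOT" (protocol 7.2.2.8.1). Dosing is on Days 1 to 21 of each 28-day cycle (6.1.1). The end-of-treatment visit is due "within 14 days following the date study treatment is permanently discontinued" (7.1.3.1), although a regular visit at which withdrawal is decided may serve instead.

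**QTcF values in use.** Table 6-3 sets rules for 481 to 500 msec and for above 500 msec, the latter labelled Grade 3. Section 7.2.3 gives a rise above 60 msec, or a new value of at least 501 msec, as an example of when to draw an unscheduled PK sample.

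**Phosphorus.** Table 6-3 handles hyperphosphatemia in mg/dL only: 5.5 as the level for restarting, above 7.0 for more than 7 days (with conditions on binder dosing), and a single-value rule, "Or if patient had a one-time serum phosphorus of > 9.0 mg/dL". SAP 7.4 uses CTCAE-grade shift tables where grades exist. Otherwise: "For laboratory parameters where CTCAE grades are not defined, shift tables using the low/normal/high/(low and high) classification". Both compare baseline with the worst on-treatment value. Neither document says which table phosphorus enters.

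**The concern.** A QT safety review needs to know how many patients had a marked prolongation at any time on study. The protocol defines what it regards as marked, but the planned ECG tables are built on other quantities: the last ECG, or the distribution at each visit. A few large individual excursions barely move a visit summary, and an excursion that has resolved by the last ECG leaves no trace in that summary.

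Phosphorus raises a similar but weaker question. It is the on-target laboratory effect of this drug, and the limits that drive management are in mg/dL. If the report groups phosphorus in categories unrelated to those limits, a reader cannot judge severity on the scale that the trial used.

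**Working it through.** The plan gives no figure to reproduce here. The check compares planned outputs with the protocol's own values and adds two illustrations.

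**1. Which scheduled ECGs fall under repeated dosing?** Take the schedule in 7.2.2.8.1 through Cycle 6 and dosing on Days 1 to 21.

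- Under repeated dosing: C1D15 and C2D15, so 2 ECGs.
- After the 7-day break: Day 1 of Cycles 2 to 6, so 5 ECGs.
- C1D1 is a baseline assessment, needed only if screening was more than 4 days earlier.
- End of treatment: 0 to 14 days after stopping, unless a regular visit takes its place.

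The last ECG is therefore usually, though not always, off drug. The plan does not say whether Day 1 ECGs come before or after the dose.

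**2. What does each planned output show about the QTcF values?**

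| Output | Patients at >=481, >500 or rise >60 msec at any time |
|---|---|
| Protocol: change to last ECG | No; one late value per patient |
| SAP: by-visit statistics | No; the maximum shows at least one patient at that visit |
| Adverse-event tables by term and maximum severity | Partly, mainly above 500 msec |
| Listings | Only by hand count |

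The by-visit table leaves the count wide open. Suppose the maximum at a visit is above 500 msec and the 75th percentile is not. Then the number of patients above 500 lies between 1 and about a quarter of those measured: 0.25 × 70 = 17.5, so 1 to 17 of 70; 0.25 × 120 = 30, so 1 to 30 of 120. Across visits, one cannot tell whether the same patient recurs. The SAP also does not say how unscheduled ECGs enter a by-visit table, and Table 6-3 calls for extra ECGs in just the patients concerned.

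**3. Illustration of size.** N = 70 to 120 comes from protocol 5.1; the SAP's 70 to 90 lies inside that range. Assume k = 3 patients, each with a QTcF excess d of 61 to 90 msec at the same visit, and all N measured. Shift in the mean = k × d / N.

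- N = 70: 3 × 61 / 70 = 2.6 msec; 3 × 90 / 70 = 3.9 msec.
- N = 120: 3 × 61 / 120 = 1.5 msec; 3 × 90 / 120 = 2.25 msec.

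A count of the same patients, with exact (Clopper-Pearson) 95% intervals:

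- 3/70 = 4.3% (0.9 to 12.0).
- 3/120 = 2.5% (0.5 to 7.1).

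**4. Phosphorus.** Protocol 1.2.1.2.1 reports elevated phosphorus in 17 of 25 phase I patients on this schedule (17/25 = 68%). If phosphorus goes into a low/normal/high table, most patients could land in one category, and values above 7.0 could not be told from values above 9.0 mg/dL. If it goes into a CTCAE-grade table, nothing in either document links a grade to those values. The gap exists on either route, but its form depends on a choice that the plan leaves open.

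**The case against.** The strongest reply is that the limits leading to action are already counted through adverse events. QTcF above 500 msec requires a dose hold, and test results that require a change in study medication are adverse events (protocol 8.1.1). SAP 7.1 counts events by preferred term and maximum severity, and events leading to dose adjustment or interruption. Since Table 6-3 labels QTcF above 500 msec as Grade 3, a Grade 3 QT row approximates that count. Hyperphosphatemia that leads to a hold is captured the same way, with a severity grade. All safety data are listed, and the specific safety event categories in SAP 7.1.1 may add more.

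Much of this stands. A reader might infer that the planned output cannot reveal any crossing of a limit; the documents do not support that. It does not close the gap, however. Under 7.2.2.8.1 only clinically significant ECG abnormalities become adverse events. At 481 to 500 msec Table 6-3 keeps the dose unchanged, so that band need not produce an event or a dose change. No table covers a rise above 60 msec.

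Three other stronger readings also fail.

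- *A QT effect would be diluted to nothing.* SAP 7.5 already gives change from baseline at C1D15 and C2D15, so a systematic on-drug shift would be visible there. Individual outliers are what is lost. Nor do the documents allow a sound figure for drug remaining at the last ECG: section 1.2.1.2.3 attributes accumulation to likely auto-inhibition of clearance, which undercuts a linear calculation.
- *Phosphorus will be reported only as low, normal or high.* Neither document says that high phosphorus has no CTCAE grade.
- *There is a QT problem to find.* The protocol reports no QTc effect in preliminary phase I data. That lowers the expected count but does not remove the need to report it, since medicines with a possible or conditional QT risk are allowed with caution (6.4.2.5).

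**Conclusion.** The point holds as a reporting gap. No planned table counts patients by worst measured post-baseline QTcF at 481 msec, 500 msec or a rise above 60 msec. Adverse-event tables and listings supply this indirectly and incompletely: best for values above 500 msec, unreliably for 481 to 500 msec, and only by hand count for the rise. The 60 msec value triggers a PK sample and is not a dosing limit, but the protocol still treats it as notable.

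The effect on a visit mean is small by construction: 1.5 to 3.9 msec for three assumed outliers among 70 to 120 patients. These are illustrations, not trial data, and if the three patients peaked at different visits the shift at each would be smaller.

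The phosphorus point is secondary and conditional. It rests on the plan not saying which shift table applies, and on neither table being tied to the mg/dL values.

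**What to change.** **QTcF (protocol 10.5.3.13 and SAP 7.5).** Replace or supplement the last-ECG summary with the maximum post-baseline QTcF per patient, taken over scheduled and unscheduled ECGs up to last dose + 30 days, in the Safety Set. Report n (%) with QTcF >=481 msec, >500 msec, and increase from baseline >60 msec, with the number of patients who have a baseline and at least one post-baseline value as denominator. Keep the by-visit summaries already planned. Record the ECG change in SAP 2.1. Exclusion criterion 17f bars a screening QTcF above 470 msec, so in eligible patients a value of 481 msec or more would be new since screening.

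**Phosphorus (SAP 7.4).** State which shift table serum phosphorus enters. Add n (%) by maximum on-treatment value: <=5.5, >5.5 to 7.0, >7.0 to 9.0, and >9.0 mg/dL. Label it a descriptive severity table, and note that it does not reproduce the more-than-7-day or binder conditions in Table 6-3. Show the cut-points in mg/dL, because protocol 10.5.3.12 converts laboratory values to SI units.

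**Cost.** Two extra tables from data already collected, assuming that unscheduled ECGs are entered in the eCRF. No new procedures and no change to any clinical rule.
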